Data Collection

Time	< 30 Days Pre-op (Baseline)	4 days Pre-Op	3 days Pre-Op	2 days Pre-Op	1 day Pre-Op	Day of Op (Pre-Op)	Recovery Area	Post- Op Day #1	Post- Op Day #30 (+/- 14 days)	Post- Op 1 Year
Patient Screening (estimated n=600)	Enrollment, Randomization, Education (n=80)	Control Continue Usual Dietary Pattern (2:5 randomization)						NPO except meds	Resume Usual Diet	Study Participation Terminates
		Dietary Restriction Protein-Calorie Restriction x 4 days (3:5 randomization)						NPO except meds		
MealLogger app Entry		X	X	X	X	X	X		→ Post Op Day 14	
Blood Draw						X	X			
CBC with diff, Chem 7, lipidomics, cortisol, epinephrine, norepinephrine, dopamine, hs CRP, IL-6, leptin, HMW adiponectin, resistin, IGF-1, P3, serum pregnancy test (as needed); pre-albumin (baseline and preop)		X								
Determinations										
Physical Activity Questionnaire	X									
24-Hour Food Recall	X									
Height, Weight	X					X	X		X	
eGFR	X					X	X			
Wound Evaluation								X		
Tissue Collection*						X				
Full Medical History	X								X	
Satisfaction Questionnaire									X	
Physical Exam	X								X	
Chart Review										X
	Preprocedure					Inpatient		Post Procedure		Registry

*discarded artery, vein, peri-vascular or subcutaneous fat, aneurysmal specimens, and amputated tissues

Dietary compliance will be measured by way of dietitian calculated intake (for data analysis will be the gold standard). The subjects will be asked to document their meals using either the MealLogger app or paper

record. The MealLogger app allows subjects to take a picture of their meals, either the ScandiShake or their routine ad libitum diet. Study dieticians will interpret dietary intake through photos and directly contact subjects using the app for clarification of intake, or through paper record if subjects are unable to use the MealLogger app. Compliance with the dietary intervention will also be evaluated through measuring expected changes in the levels of plasma amino acids using an LC-MSMS platform, and insulin-like growth factor-1 (IGF-1) by ELISA. Because free amino acids are not stored in the body, PCR results in a rapid decline of essential amino acids, including methionine and tryptophan, that are monitored easily in blood plasma^{79, 80}. Isolated protein restriction also results in reduced plasma IGF-1, even in the absence of overall PCR⁸¹.

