H_2S and H_2S production capacity (two distinct entities, see *Cell* paper¹¹) will be longitudinally measured, as will stress and safety markers in blood samples taken prior to dietary intervention (PCR or control), after the dietary intervention but before surgery, and sequentially after vascular surgery. Blood samples will also be collected and analyzed by [name] team at Northwestern to assess for changes related to PCR. Adipose tissue biopsies from fat depots (subcutaneous, perivascular) will be taken at the time of surgery and analyzed for the effects of diet on lipid composition and on inflammatory markers predictive of the response to surgical stress. Additionally, discarded specimens (discarded artery, vein, peri-vascular or subcutaneous fat, aneurysmal specimens, and amputated tissues) will be collected and stored for microscopic analysis. Enrolled patients and their clinical data will be entered into a study-specific database within REDCap.

Statistical Considerations

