The focus of this Mechanistic Trial is to gain insights into practical future trial construction considerations such as patient compliance and physiologic impact. We anticipate that the supervised PCR will be completed by a majority (~80%) randomized to that arm and that H_2S and H_2S production capacity will rise on day two and be significantly elevated above baseline until re-feeding POD#1. We expect that markers of stress will change significantly less in the active treatment group compared to normal diet group. Using an α of 0.05 and β of 0.8, based on the differentials observed in rodent work and factoring in non-compliance, via intent-to-treat the study is powered to test these two primary scientific markers (H_2S and norepinephrine/IL-6). Furthermore, we believe that there will be no significant adverse effects of the H_2S upregulation and PCR diet but do expect a 20% dietary compliance failure rate. Based on our own pilot work, we anticipate that markers of inflammation will be elevated (compared to non-atherosclerotic patient's samples in hand) in the enrolled subjects and further amplified by the surgical stress. We anticipate that the blood and adipose phenotypic signatures will have high inflammation, but that the subjects compliant with PCR will have a reduced global inflammatory activation state, and trends toward less carotid plaque inflammation and fewer postoperative complications. Our key endpoint for upregulation of endogenous hydrogen sulfide will be the P3 cell sorting assay. Based on pilot data we anticipate a 4% increase in the PCR diet cohort compared to ad lib diet controls, with an expected standard deviation of 8%. Using a power of 80% and an alpha of 0.05, and 8% specimen loss rate we need a sample size of $n=80$ to reach statistically meaningful conclusions (un-paired T-test). Importantly for future trials, we anticipate that the unbiased discovery platform will generate novel mechanistic hypotheses founded on human data and tissues that will be ripe for future research and translation.

References

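### The key P3 comparison should be one prespecified ANCOVA on the pre-diet value, not an unpaired t-test whose outcome and sample are left open

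*Combined protocol and SAP*

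**What the plan says.** Statistical Considerations states: "Our key endpoint for upregulation of endogenous hydrogen sulfide will be the P3 cell sorting assay". The planning assumption is "we anticipate a 4% increase in the PCR diet cohort compared to ad lib diet controls, with an expected standard deviation of 8" percent, with 80% power, alpha 0.05 (sidedness not given) and 8% specimen loss. The total of 80 is said to be enough "to reach statistically meaningful conclusions (un-paired T-test". No other test is named for P3.

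The same section expects that hydrogen sulfide and its production capacity "will rise on day two and be significantly elevated above baseline until re-feeding POD#1". That expectation is relative to baseline, whereas the planning assumption is a contrast between arms.

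Data Collection plans "blood samples taken prior to dietary intervention (PCR or control), after the dietary intervention but before surgery, and sequentially after vascular surgery" for hydrogen sulfide and its production capacity. The second primary endpoint under Project Goals/Specific Aims gives the same three stages. The blood panel in the Data Collection table includes P3 ("IGF-1, P3, serum pregnancy test (as needed); pre-albumin (baseline and preop"), and the baseline column is headed "< 30 Days Pre-op (Baseline". The draws at which P3 itself is assayed could not be read reliably from that table. Recruitment lists baseline testing among the steps that randomization is meant to precede.

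**The concern.** A pre-diet measurement of the key marker is very probably collected, but the named test ignores it. If P3 before the diet predicts P3 after it, adjustment removes variance at almost no cost. This matters because the unadjusted test is weak on the plan's own inputs.

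The words unpaired t-test also fit more than one analysis: final value or change from baseline, before surgery or at an early postoperative draw. If the choice is made after the data are seen, the 5% error rate is no longer assured. The trial is meant to inform the construction of later trials, so an ambiguous P3 result would carry forward.

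**Working it through.** **Inputs from the plan.** 48 and 32 randomized (3:2, Approach and Methods); 8% specimen loss; difference 4; SD 8; alpha 0.05, taken here as two-sided. Evaluable: 48 × 0.92 = 44.2 and 32 × 0.92 = 29.4, so 44 and 29.

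**Input not in the plan.** The correlation r between pre-diet and post-diet P3. It is assumed, and a range is shown.

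**The plan's own figure.** For standardized difference 4/8 = 0.5, a two-sided unpaired t-test at 3:2 needs 133 evaluable patients for 80% power, and 133/0.92 gives 145 enrolled. The stated 80 is not reproduced. That is a separate defect, noted because ANCOVA might be offered as its cure.

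**t-test power.** Noncentrality = 0.5 × √(44 × 29/73) = 2.09 with 71 df, giving power 54%.

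**ANCOVA power.** Noncentrality = (4/residual SD) × √(44 × 29/73) × √(69/70), with 70 df. The last factor charges for expected baseline imbalance.

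- If 8 is the SD of a single value, residual SD = 8√(1 − r²).
- If 8 is the SD of change, the single-value SD is 8/√(2(1 − r)), so residual SD = 8√((1 + r)/2). On this reading the 54% belongs to the t-test on change.

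| r | Residual SD, single-value reading | Power | Residual SD, change reading | Power |
|---|---|---|---|---|
| 0.3 | 7.63 | 57% | 6.45 | 72% |
| 0.5 | 6.93 | 66% | 6.93 | 66% |
| 0.7 | 5.71 | 82% | 7.38 | 60% |

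At r = 0 on the single-value reading, ANCOVA has 53.5% against 54.1% for the t-test. The two are equal at r of about 0.12. Reaching 80% on that reading needs r of about 0.68.

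**Non-compliance.** The plan says investigators "do expect a 20% dietary compliance failure rate". If the 4 does not already allow for this, and non-compliers get no effect (an assumption), the difference is 4 × 0.8 = 3.2. The t-test then has 38% power. ANCOVA has 40%, 47% and 63% on the single-value reading, or 53%, 47% and 43% on the change reading, at r = 0.3, 0.5 and 0.7.

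**Error from choosing the outcome afterwards.** With equal variances, the final-value and change-score statistics have correlation √((1 − r)/2) under the null. Two selection rules differ:

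- *Smaller p-value, either direction.* The chance that at least one test rejects is 8.3%, 8.8%, 9.1% and 9.4% at r = 0, 0.3, 0.5 and 0.7. Simulation with 44 and 29 patients gave 8.3% to 9.3%.
- *Result more favourable to the restricted diet.* A false claim of benefit has probability 2.5% + 2.5% − P(both reject for benefit). This is 4.2%, 4.4%, 4.5% and 4.7% at the same r, against 2.5% for one test. A false finding of harm then needs both tests to reject for harm, which by symmetry has the same probability as both rejecting for benefit. The two terms cancel and total two-sided error stays at 5%.

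**The case against.** **Any single named analysis restores 5%.** This is true. One sentence fixing the t-test on the pre-surgery value would control the error. The case for ANCOVA is precision, and that depends on an unstated r, which a baseline up to 30 days before surgery could lower. ANCOVA is also not best in every setting: with assumed slopes of 1.3 and 0.8 in the two arms, simulated power was 77.0% to 77.7%, against 77.9% for the change-score t-test. That loss is small. In the same setting the final-value t-test had 33.1%.

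**ANCOVA does not itself fix the draw or the unit.** This stands, so the wording must name both.

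**Baseline may follow an unblinded assignment.** This stands too. Patients know whether they are on shakes or usual food. A baseline drawn after they learn this could be affected by arm, in its value or in whether it is missing.

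**The plan already claims to allow for non-compliance under intention to treat.** It does, but in a sentence about differentials seen in rodents. Whether that covers the human 4% is unclear, so the diluted figures are conditional.

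**Stronger readings a reader might infer.** One is that picking the favourable result gives about 9% two-sided error. It does not; that figure needs selection in both directions and this particular pair of outcomes. For absolute against relative change, or raw against log values, simulation under assumed lognormal data gave only about 6–7%. Another is that selective reporting is planned, or that the t-test is invalid. Nothing in the documents says the first, and a t-test fixed in advance is valid.

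**Conclusion.** The point holds as a recommended improvement. The named test leaves a planned baseline unused and does not identify the outcome or sample. On the plan's inputs, ANCOVA raises power from 54% to between 57% and 82% over r = 0.3 to 0.7, depending on r and on which SD the 8% is. The worst loss is about half a point.

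The conclusion rests on P3 being assayed before the diet (inferred), on r above about 0.12 for a gain over a final-value t-test, and on broadly similar baseline slopes in the two arms. Fixing one analysis also removes the scope for about 8–9% error under two-directional selection, or for false claims of benefit of about 4–5% instead of 2.5% under selection towards the diet.

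A reader might conclude that adjustment rescues the sample size. The documents do not support this: they give no r, and 82% is the top of an assumed range. ANCOVA must not be used to justify n=80 or the stated 80% power.

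**What to change.** Before any comparison by arm, add to Statistical Considerations:

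- **Primary P3 analysis:** intention-to-treat ANCOVA of the post-diet, pre-surgery P3 value on arm and pre-diet P3, two-sided 5%.
- **Sensitivity analysis:** the unpaired t-test on the same post-diet, pre-surgery sample.
- **Covariate:** a sample taken before the assigned diet starts and, where possible, before the patient learns the assignment.
- **Missing data:** report missing pre-diet and post-diet P3 by arm.
- **Units and assumptions:** state whether 4% is percentage points or relative, whether 8% is the SD of a single value or of change, and whether the 4% already allows for non-compliance.

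Robust standard errors, and setting a missing baseline to the overall mean, are optional. The second is safe only if baseline is unaffected by assignment.

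Confirm that P3 is run on the pre-diet sample. If it is not, name the unpaired t-test on the post-diet, pre-surgery value as the single primary analysis.

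The cost is wording and one degree of freedom if the pre-diet assay is already planned. Drawing baseline before the assignment is disclosed may also need a change in the order of visits.
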